## 2.1 Device Overview (LED light source)

The core component of the device is an LED light source emitting at two wavelength ranges. These wavelengths are red light at 630-680 nm (primary wavelength) and blue light at 450-470 nm (ancillary wavelength). The light source transfers energy to the infected region of the nails to break down fungus cells.

The light source operates with an accessory photosensitizer formulation based on the well-known aniline dye “methylene blue”. Methylene blue (MB) has been approved by Health Canada for several other indications, although not for the specific treatment of onychomycosis. In the ToeFX Light Therapy device, MB acts as a photosensitizer, mediating the transfer of energy from the red LED light source to the fungus. The MB concentration is 0.5%.

The mode of action is as follows: upon application of light, the photosensitizer molecule absorbs energy to form a short-lived excited state. The excited-state molecule rapidly transfers energy to surrounding oxygen to produce reactive oxygen species (ROS), which selectively disrupt the fungal cells. These ROS are short-lived and the reaction ceases immediately upon deactivation of the light.

The light device and photosensitizer formulation are used in conjunction. The formulation is painted onto the surface of the affected nail and allowed to penetrate into the nail bed for 10 to 15 minutes. Red light at an intensity of 200 mW/cm^2 is subsequently applied to the same area for 4 to 6 minutes. The nail may also be exposed to blue light at an intensity of 200 mW/cm^2. The blue light has no effect on the photosensitizer and is of secondary importance; however, several research groups have confirmed that exposure to mild blue light can have anti-inflammatory effects (Refer to Section 6.02, “Previous Studies”).

The treatment is administered 12 times over the course of 1 year. The light device has an expected lifetime of several thousand hours and is designed to dissipate ambient heat.

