## 2.2 Procedural workflow

A foot care clinician applies a photosensitizer topically to infected toenails; the toenails are then exposed to the ToeFX light source for about 15 minutes. The patient visits the clinic to repeat the process at intervals of two weeks.

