### 3.2 Study Design

Study Type:	Interventional (clinical trial)
Actual Enrollment:	100 participants
Masking:	None (Open Label)
Primary Purpose:	Treatment
Study Start Date:	Immediately upon approval by Health Canada

Arm	Intervention/treatment
Arm 1 Red light only	Core technology. Formulation and red light only. Apply photosensitizer; allow to penetrate for 15 minutes; apply red light for 15 minutes.
Arm 2 Red and blue light	Apply photosensitizer; place foot under blue light and allow to penetrate for 15 minutes. Apply red light for 15 minutes.

Arm 1 will test the core technology of the ToeFX system; this study reproduces protocols described in the literature (see ‘Previous Studies’ in Section 6.02). Arm 2 pairs the core technology with application of blue light. After application of the formulation, the nail is exposed to blue light at a wavelength of 450-470 nm and an intensity of 200 mW/cm^2. The blue light has no effect on the photosensitizer; however, several research groups have confirmed that exposure to mild blue light can have anti-inflammatory effects that would improve patient

outcomes (see ‘Previous Studies’ in Section 6.02). We will assess whether inclusion of blue light in the protocol affects the clinical outcome.

Debridement should be done prior to each treatment. Debridement should not be carried out more proximally than the most proximal margin of the dystrophic nail, as this can interfere with assessment of clear nail area attributable to the device intervention. Clinician should debride the nail and apply the photosensitizer formula and let it penetrate for 15 minutes, then if applicable apply the blue light (450-470 nm). Apply the red light (640 nm) for 15 minutes. The treatment is administered 12 times over the course of 1 year.

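### Section 3.2 gives two incompatible blue-light timings for Arm 2; under the sequential one, the blue-light comparison is confounded with dye contact time

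*Combined protocol and SAP*

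**What the plan says.** All the text on the order of blue light is in section 3.2 (Study Design) of the combined protocol and SAP.

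- **Arm 1 row:** "allow to penetrate for 15 minutes; apply red light for 15 minutes".
- **Arm 2 row:** after the photosensitizer is applied, "place foot under blue light and allow to penetrate for 15 minutes", followed by 15 minutes of red light. Blue light and penetration share the same 15 minutes.
- **Paragraph below the table:** "After application of the formulation, the nail is exposed to blue light". This says only that blue light follows application of the dye, which is true of either order.
- **Operator instruction at the end of the section:** "let it penetrate for 15 minutes, then if applicable apply the blue light (450-470 nm", and then red light for 15 minutes. Here blue light comes after penetration, and its duration is not given.

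The same section states the purpose of the second arm: "We will assess whether inclusion of blue light in the protocol affects the clinical outcome".

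Two earlier sections also give timings. Section 2.1 (Device Overview) has the dye "allowed to penetrate into the nail bed for 10 to 15 minutes", after which red light at 200 mW/cm² "is subsequently applied to the same area for 4 to 6 minutes". In section 2.2 (Procedural workflow), "the toenails are then exposed to the ToeFX light source for about 15 minutes". Neither section gives the order of blue light relative to penetration.

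**The concern.** Blue light is given either during the 15 minutes of penetration or after them. The arm table says during, the operator instruction says after, and no text ranks one above the other. The operator instruction is not a stray remark. It is the step-by-step direction to the clinician, and its conditional wording shows that it is meant to serve both arms, so a site could reasonably follow it.

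If a site does, Arm 2 differs from Arm 1 in two respects at once: blue light, and extra time with dye on the nail before red light. Arm 1 has no matching wait. A difference between arms could then come from either factor. The analysis of variance in section 3.4 has terms for treatment and pooled center only and could not tell them apart. If the three sites read the text differently, Arm 2 becomes a mixture of two regimens that varies by site.

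Dwell time is not obviously irrelevant to the mechanism. Section 2.1 treats penetration as a timed step and describes the dye as the agent through which red light acts on the fungus. The protocol's statement that blue light does not affect the photosensitizer does not help, because the issue is contact time rather than an interaction between light and dye.

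**Working it through.** There is no stated power or sample-size figure to reproduce on this point. The check is a comparison of texts and simple arithmetic.

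**Dye contact before red light**

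Inputs:
- Penetration time P = 15 minutes in both arms (section 3.2).
- Blue-light time after penetration, b: 0 under the Arm 2 row; not stated in the operator instruction. *Assumed* range 5 to 15 minutes. The upper end is the only blue-light time in the documents (Arm 2 row); the lower end is an assumption.

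Formula: contact before red light = P + b.

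| Regimen | Contact before red light | Ratio to Arm 1 |
|---|---|---|
| Arm 1 | 15 min | 1.0 |
| Arm 2, arm table | 15 + 0 = 15 min | 15/15 = 1.0 |
| Arm 2, operator instruction, b = 5 | 15 + 5 = 20 min | 20/15 = 1.33 |
| Arm 2, operator instruction, b = 15 | 15 + 15 = 30 min | 30/15 = 2.0 |

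For any b above zero, Arm 2 has the longer contact, so the existence of the imbalance does not depend on the assumed range. A lower end of 4 minutes would give 19 minutes (19/15 = 1.27). The sequential figures also lie 5 to 15 minutes beyond the 15-minute upper end of the penetration range in section 2.1.

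The documents do not describe removing the dye before red light. If it stays on through the 15-minute red exposure, total contact is 20 + 15 = 35 to 30 + 15 = 45 minutes against 15 + 15 = 30, or 1.17 to 1.5 times.

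**Blue-light dose**

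Section 3.2 gives 200 mW/cm² for blue light. Over the arm table's 15 minutes this is 0.2 W/cm² × 900 s = 180 J/cm². The operator instruction fixes no dose; an assumed 5 minutes would give 0.2 × 300 s = 60 J/cm².

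**Red-light timing (a separate conflict)**

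Section 2.1 gives 4 to 6 minutes of red light and section 3.2 gives 15. Section 3.2 states no red irradiance. If the 200 mW/cm² in section 2.1 applied to both:
- Section 2.1: 0.2 × 240 s = 48 J/cm² to 0.2 × 360 s = 72 J/cm².
- Section 3.2: 0.2 × 900 s = 180 J/cm².
- Ratio: 180/72 = 2.5 to 180/48 = 3.75.

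The doses would be equal if the 15-minute regimen ran at 48/900 = 0.053 to 72/900 = 0.080 W/cm², that is, about 53 to 80 mW/cm². Section 3.2 gives both arms the same red time, so this conflict does not separate the arms. It arises only if a site works from section 2.1.

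**The case against.** The strongest reply is that the confounding depends on the less likely reading. The Arm 2 row is the explicit arm definition, gives a blue-light duration and matches Arm 1's timing. On that reading contact is equal and only a wording inconsistency remains. This is fair as to likelihood, but nothing makes the row govern, and the conflicting text is the instruction a clinician would carry out.

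Second, no effect on outcome is shown, and the lower bound for blue-light time is assumed. Both points stand. They limit what can be said about size, but not the fact that the two factors would be inseparable.

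Third, the comparison is not the primary one. Success is judged by a lower confidence bound on the response rate (section 3.4) and against a published rate (section 3.3), and section 2.1 gives blue light a secondary role. This also stands and keeps the point from being graded higher. Even so, the blue-light assessment is a stated aim, and finalizing the treatment protocol is a study objective (section 3.0), which requires knowing what was delivered.

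Fourth, the blue-light question could be read as comparing whole regimens, with added time part of the package. That reading is possible, but it would still require a single defined regimen. The documents also describe no random allocation to arms, so causal interpretation is limited in any case. Equalising dwell does not repair that; it removes one avoidable source of ambiguity.

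Finally, site training (section 6.2) and the clinician's description of the protocol used (section 3.1) make divergence easier to notice. They do not say which text is correct.

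**Conclusion.** The concern holds. The contradiction within section 3.2 is certain. The confounding is conditional: it occurs wherever the operator instruction is followed as written, and then arm and dwell time are fully aliased. With blue light assumed to last 5 to 15 minutes, contact before red light is 5 to 15 minutes longer in Arm 2; under the arm table the difference is zero. Whether the extra dwell would change response cannot be judged from the documents, so neither the direction nor the size of any bias can be given. The red-light conflict with section 2.1 is real but does not bias the comparison of arms, and its 2.5- to 3.75-fold figure holds only if the same irradiance applies to both regimens. The point should be fixed, but it does not threaten the primary endpoint.

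**What to change.** In section 3.2, state one regimen per arm: penetration minutes, blue-light minutes and their timing, red irradiance and red minutes. Make the time from dye application to the start of red light identical in both arms. The simplest way is to keep blue light within the 15-minute penetration, as in the Arm 2 row, and delete the sequential sentence. If blue light after penetration is preferred, state its duration and give Arm 1 an equal light-off wait before red light.

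Align sections 2.1 and 2.2 with the chosen regimen. On the case report form, record for each session the minutes of dye contact before red light, of blue light and of red light, so that any departure can be seen in the data.

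The cost is amendment wording and a few form fields. No extra subjects or visits are needed.

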### **3.3 Control**

Our study cohort will be compared to known values published in a large multicenter trial of the topical solution Jublia (manufactured by Valeant). Jublia is a once-daily treatment of 10% w/w efinaconazole for the treatment of onychomycosis. Jublia showed a complete cure rate of 15-18% in a study of two groups of 800 patients.

We will follow the inclusion and exclusion criteria defined in the Jublia trial. Patients in the Jublia study showed 20% to 50% clinical involvement of the area of the target great toenail, without dermatophytomas or lunula (matrix) involvement. Patients had positive dermatophyte culture and positive potassium hydroxide (KOH) examination from the target toenail and were not excluded for concomitant *Candida* infection. Patients were assessed for clear nail.

Based on previously published studies of photodynamic therapy for onychomycosis, we expect to observe a complete cure rate on the order of 50-80%. Given the large difference in the observed cure rate for Jublia and the anticipated cure rate for the ToeFX Light Therapy device, a sample size of 100 patients is adequate to establish statistical significance of our results.

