## 1.0 Protocol Summary

Title	A Pilot Study Evaluating the Feasibility and Usability of ToeFX Light Therapy Device for Mild to Moderate Distal Subungual Onychomycosis (DSO) of the Toenail
Short Title	ToeFX light therapy pilot
Methodology	Open label, prospective, multi-site, multi-investigator
Study Sites	
Hamilton Foot Clinic [name]
 
Bruyere Foot Specialists [name]
 
Wilson Foot Clinic [name]

Number of Study Subjects	100 subjects
Diagnosis and Main Inclusion Criteria	
Healthy males or females who meet the following criteria:
 
 
• are between 18-75 years of age.
 
• have a clinical diagnosis of mild to moderate DSO in the nail of at least one great toe, with 20% to 50% clinical involvement of the target toenail, without dermatophytomas or lunula (matrix) involvement, without lunular or proximal involvement.
 
• exhibit positive mycology results (ie, KOH test and culture of a dermatophyte) from the target great toenail, confirming common dermatophytes such as T. rubrum.
 
• are willing to abstain from any other treatment for onychomycosis for the duration of the pilot study.
 

Study Product and Planned Use	The ToeFX Light Therapy system is intended as a safe, effective and non-invasive treatment for nail fungus.

	This device will be used in accordance with the attached protocol. This study will be an open-label, prospective pilot study. The subjects will be 100 patients with mild to moderate onychomycosis. The purpose of the study is to establish the efficacy of the ToeFX device, which has shown compelling results in in vitro and ex vivo (cadaver) studies but has not been tested in patients.
Primary Endpoint	Technical Success: We will monitor (a) whether subjects attain 3 mm or more of clear nail growth post-treatment (b) whether subjects show mycological cure of their infection, as verified by culturing.
Secondary Endpoints	
 
• Usability and form factor reported by clinicians
 
• Satisfaction with the treatment reported by patients
 

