### **3.4 Outcome Measures**

Clear nail: The specifications for clear nail are described below. The 95% one-sided confidence interval (i.e., lower bound only) around the observed response rate as described below should be  $\geq 50\%$ .

We will monitor whether subjects attain 3 mm or more of clear nail growth post-treatment. We will verify by taking a photograph prior to every treatment to assess the change in millimeters (mm) of clear nail bed. Millimeters (mm) of clear nail from the base of the toenail will be determined from digital photographs of the toenail and verified via software. The change in mm of clear nail bed will be calculated as the difference in mm of clear nail bed from baseline measurement to the measurement at the end of the procedure administration phase.

An increase in mm of clear nail between the two measurement points indicates that the toenail has improved and is positive for study success. A decrease in mm of clear nail between the two measurement points indicates that the toenail has worsened and is negative for study success.

Individual toenail success criterion is defined as 3 millimeter (mm) or more of clear nail growth as evaluated relative to baseline.

Length of the unaffected part of the target nail is measured in millimeters along the midpoint from the nail fold to the proximal border of the affected part (lowest point affected) along the midpoint of the target nail. Change from Baseline is: (Baseline value subtracted from 6-month treatment value). P-value shall be based on analysis of variance (ANOVA) with treatment and pooled center. Statistics will be provided for the adjusted least square mean.

To ensure adequate photographic quality and to maximize our ability to compare photographs across timepoints and across subjects, a standardized photography protocol will be put in place. Photographs shall be of high quality and high resolution. An internal scale (e.g. ruler) will be included in all images to allow objective measurement of millimeters of clear nail regardless of magnification of the image.

**Mycology:** Among toenails which are deemed responders based on the “clear nail” criteria, we will also assess for negative mycology (negative stain with concurrent negative culture, or two negative cultures from the same nail).

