### **3.6 Data Analysis**

- Descriptive statistical analysis to analyze degree of response (e.g., complete response or clearing, >75% clear, 50-75% clear).
- Increase in clear nail at each timepoint of evaluation after the last treatment
- Increase in clear nail as a function of the number of treatments

To evaluate the overall response rates, we plan to ensure that the study report be presented in a tiered fashion, citing the success rate for the subjects exhibiting mycological cure concurrent with clear nail, with separate presentation of the data for subjects exhibiting mycological cure with residual nail dystrophy.

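### The external control is a complete cure rate, but complete cure is neither defined nor an endpoint, so the plan yields no rate that matches it

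*Combined protocol and SAP*

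**What the plan says.** **Control and sample size (section 3.3).** "Our study cohort will be compared to known values published in a large multicenter trial of the topical solution Jublia". The only published value given is a complete cure rate: "Jublia showed a complete cure rate of 15-18% in a study of two groups of 800 patients". The anticipated device result is put in the same terms: "we expect to observe a complete cure rate on the order of 50-80" per cent. From the gap between the two, section 3.3 concludes that "a sample size of 100 patients is adequate to establish statistical significance of our results".

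**Success (section 3.4).** "Individual toenail success criterion is defined as 3 millimeter (mm) or more of clear nail growth as evaluated relative to baseline". The one numerical requirement, a one-sided 95% lower confidence bound of at least 50%, attaches to this response rate. A looser sentence in the same section treats any increase in clear nail as meaning that "the toenail has improved and is positive for study success". Negative mycology is to be assessed among toenails already classed as clear-nail responders.

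**Primary endpoint (section 1.0).** Two components are listed, "a) whether subjects attain 3 mm or more of clear nail growth post-treatment (b) whether subjects show mycological cure of their infection", with no rule for combining them.

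**Reporting (sections 3.1 and 3.6).** Section 3.1 asks for a table of complete, partial and non-responders without defining complete. Section 3.6 offers complete response or clearing as an example of a descriptive category. It also plans tiered reporting, "citing the success rate for the subjects exhibiting mycological cure concurrent with clear nail", with mycological cure plus residual dystrophy shown separately.

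**The concern.** The trial has no concurrent untreated or standard-treatment arm; both arms receive the device. Any statement that the device does better than existing treatment therefore rests on the published 15-18%. That figure is a complete cure rate, and the plan defines no device rate of the same kind. The rate it does define, a 3 mm gain, is a different outcome and usually an easier one.

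Two things are at stake. First, the comparator for the published figure can be chosen after the results are known, in an open-label study whose stated purpose is to establish efficacy. Second, if the choice falls on the 3 mm rate, an apparent advantage could come from the difference in definitions and not from the device.

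**Working it through.** **1. The plan's own figure, N=100.** Section 3.3 states no alpha, power or test, so 100 cannot be reproduced as the output of a formula. Its adequacy can be checked. For an exact one-sample binomial test of a true 50% against 18% (the least favourable pair in the stated ranges), the minimum n is about 19 for 80% power and 26 for 90% power at one-sided 2.5%, or 17 and 21 at one-sided 5%. On cure against cure, 100 is more than enough.

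**2. The formal bar on the 3 mm rate.** With n=100, a one-sided 95% lower bound of at least 50% requires 59 responders (exact bound 50.3% at 59/100 and 49.3% at 58/100). The Wilson and Wald limits give the same count. This bar is well above 18%, but it concerns partial improvement.

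**3. How far a 3 mm gain is from a clear nail.** Inputs: entry involvement f of 20-50% (section 3.5) and the 3 mm threshold (section 3.4). Nail length L is not in the documents; 12 and 15 mm are assumed. The border is taken as straight, so that area involvement can be read as length.

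Affected length = L × f. Residual involvement after a 3 mm gain = (L × f − 3)/L.

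| f | L = 12 mm: affected, residual | L = 15 mm: affected, residual |
|---|---|---|
| 50% | 6.0 mm, 25% | 7.5 mm, 30% |
| 35% | 4.2 mm, 10% | 5.25 mm, 15% |
| 25% | 3.0 mm, 0% | 3.75 mm, 5% |
| 20% | 2.4 mm, 3 mm gain not attainable | 3.0 mm, 0% |

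At 50% involvement a success would still lie inside the 20-50% entry range. At 35% it would be below that range but not clear. At 20% on a nail shorter than 15 mm, a fully cleared nail cannot gain 3 mm and scores as a failure. The 3 mm rule therefore cannot stand in for cure in either direction.

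**4. What a mismatched comparison would do.** Take a device whose true complete cure rate is 18%, no better than the upper published figure. An exact one-sided 5% test against 18% with n=100 rejects at 25 or more.

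- Like for like, the chance of rejecting is 4.96%.
- If the 3 mm rate is counted instead, and its true value is assumed to be 30% or 40%, the chance is 88.6% or 99.9%.

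At one-sided 2.5% (27 or more), the corresponding figures are 1.7%, 78% and 99.8%.

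**5. The matched comparison.** Complete cure against 18%, n=100, one-sided 5%, at least 25 cures: power is 88.6% at a true 30%, 98.8% at 35% and above 99.9% at 50%.

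**The case against.** A reader might infer that the plan does set the 3 mm rate against 15-18%, so that the headline comparison favours the device by definition. The documents do not support that reading.

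- No section says that the 3 mm rate is the one to be compared. Section 3.3 words both sides as complete cure. Equally, no section rules the 3 mm rate out.
- The direction of bias is not fixed by definition. Near 20% involvement on a short nail the 3 mm rule is harder to meet than full clearance, and dropouts count as failures.
- The only numerical success rule is the 50% lower bound, not 15-18%.
- Mycological cure is part of the primary endpoint, and sections 3.1 and 3.6 plan descriptive outputs on complete response. Because section 3.6 contrasts clear nail with residual dystrophy, clear nail there may mean no residual dystrophy. Section 3.4, however, uses the same term for its 3 mm criterion, so the 3 mm reading is also open. A trial with no fully clear nail would probably show this in its complete-responder table.

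All of this stands, and it makes the point conditional. It does not remove it. The complete-responder table has no definition, the descriptive clearing category does not mention mycology, and the tier's clear nail can be read two ways. None is tied to the published rate. The 50% rule, even when met, says nothing about complete cure.

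It is also fair to object that using 18% as a constant ignores sampling error in the published rate. The effect is small: a normal-approximation two-sample comparison (two-sided 5%) of 100 subjects with 400 to 1600 controls has power 74% to 81% for 30% against 18%, close to the 78% of the one-sample test at one-sided 2.5%.

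**Conclusion.** The concern holds in conditional form. The plan names a complete-cure benchmark and sizes the trial on an expected complete cure rate, but it defines no complete-cure endpoint to put beside that benchmark. If the 3 mm rate, with or without negative mycology, fills the gap, the comparison is not like for like and will generally favour the device. That the plan already makes this comparison, or that it favours the device by definition, goes beyond the text.

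The 25-30% residual involvement is for nails at the 50% upper limit of entry and rests on an assumed length of 12-15 mm and a straight border. The error rates in step 4 rest on assumed 3 mm response rates of 30% and 40%, since the documents give none. The sample size is not in question. Because complete cure could otherwise be defined after open-label results are seen, the definition should be fixed beforehand.

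**What to change.** 1. In sections 3.4 and 3.6, define complete cure as 0% clinical involvement of the target nail together with negative mycology, counted over all enrolled subjects with dropouts as failures.
2. Obtain mycology at the final assessment for every fully clear nail as well as every 3 mm responder. As written, section 3.4 would leave fully cleared nails that gained less than 3 mm without the result needed to count as cures.
3. Compare only this complete cure rate with the published one, by an exact one-sided 5% binomial test against 18%, the upper end of the stated range (at least 25 of 100).
4. State the assessment time used here and the published one, and report any difference as a limitation. The published time is not in the documents, and section 3.4 gives both a 6-month value and an end-of-administration value for the 3 mm change.
5. Judge the 3 mm rate only against the 50% criterion, and say in section 3.3 that it is not compared with 15-18%. State in section 3.6 what clear nail means in the tiered report.

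Cost: protocol wording, one further analysis, a few more mycology samples, and a headline rate that is likely to be lower than the 3 mm rate. N=100 does not need to change.
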